Diagnosis and Main Inclusion Criteria	Patients with renal biopsy consistent with membranoproliferative glomerulonephritis with monoclonal immune deposits or C3 glomerulonephropathy in addition to positive serum studies for monoclonal gammopathy within 5 years of enrollment
Study Product, Dose, Route, Regimen	For the main study, daratumumab infusions are at a dose of 16 mg/Kg once weekly for 8 doses followed by once every 2 weeks for an additional 8 doses. Patients in open-label extension (OLE) who relapse will receive 12 additional doses of daratumumab(16 mg/kg). The first 8 doses will be administered weekly and the last 4 will be given every other week.
Duration of Administration	6 months for main trial and the OLE includes a maximum of 3 courses over 24 months
Reference therapy	No reference therapy
Statistical Methodology	The incidence of treatment emergent major infection, grade 3 or 4 anemia, leukopenia or thrombocytopenia will be summarized. A paired t-test will be performed for changes in HgB, WBC count and platelet count from Baseline (Day 0) to 6 month and 12 month timepoints

1 Introduction

This document is a protocol for a human research study. This study will be carried out in accordance with the applicable United States government regulations and Mayo Clinic research policies and procedures.

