7.1 Sample Size Determination

This is a proof-of-concept study and therefore a power calculation was not performed. The primary endpoint of this study is the safety of this drug in terms of incidence of rate of treatment emergent major infection, grade 3 or 4 anemia, leukopenia or thrombocytopenia in patients with PGNMID and C3 GN associated with monoclonal gammopathy and the secondary endpoint is to the efficacy of daratumumab in this patient population. A paired t-test will be utilized to test the hypotheses described below. Twelve subjects will be enrolled in the study.

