7.2 Statistical Methods

Descriptive Statistics

Univariate descriptive statistics and frequency distributions will be calculated, as appropriate for all variables. Baseline values for demographic, clinical, and outcome variables (primary and secondary) in each response category will be tabulated. Time-to-response will be analyzed descriptively with Kaplan-Meier method.

For the primary endpoint, the number and proportion of patients with treatment-emergent major infections, grade 3 or 4 anemia, leukopenia or thrombocytopenia will be summarized. Changes in Hgb, WBC count and platelet count from baseline (Day 0) will be analyzed through a paired t-test by comparing post-baseline to baseline values. The secondary endpoint of the proportion of patients with complete or partial response will be summarized in a similar manner.

It is expected that 9 patients will enter the OLE. The rate of relapse in addition to the time to relapse from the last dose of daratumumab to initiation of retreatment will be evaluated. Paired t-test will be used to evaluate change in the proteinuria from time of relapse to the end of the study. Rate of CR and PR will be evaluated at the end of the OLE.

Handling of Missing Data

This is a study of only 12 patients and expect that majority of patients will have complete data available.

Primary Hypothesis: Daratumumab is safe and well-tolerated in patients with PGNMID and C3GN associated with monoclonal gammopathy

To test this hypothesis, the incidence of major infection will be examined, specifically the development of pneumonia, severe urinary tract infection/pyelonephritis, sepsis, meningitis will be reported. In addition, anemia, leukopenia, thrombocytopenia will be examined by evaluating changes in Hgb, WBC count and platelet count, respectively. Statistical significance will be assessed using paired t-test comparing 6 months and 1 year value compared to baseline. The

number of patients who had to discontinue drug due to side effect (drop in blood counts, infection) will also be reported.

Secondary Hypothesis: Daratumumab is effective in inducing remission (defined as improvement in proteinuria and eGFR) in patients with PGNMID and C3GN associated with monoclonal gammopathy

A paired t-test will be performed to assess change in proteinuria and renal function at 6 months and 12 months compared to baseline (screening visit).

Interim Analysis

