7.2 Subject Population(s) for Analysis

All-treated population: Any subject that received at least one dose of study drug.

8 Safety and Adverse Events

The primary side effects associated with daratumumab include anemia, neutropenia and thrombocytopenia and these will be evaluated initially by monthly CBC done on Day 21, 49, 77, 105, 133, 161 and then every 3 months done on Day 264, 365. Further, these will be evaluated during OLE laboratory assessments.

Other side effects include risk of infection specifically pneumonia and patients will be asked about any signs of symptoms suggestive of infection (e.g fever, cough) or any hospitalization, emergency department visits or other doctor visits at the clinical visits on Day 49, 77, 133, 161, 264, 365 and during OLE when laboratory assessments are completed or an infusion is administered. Other side effects include symptoms of nausea and fatigue and similarly patients will be asked regarding these symptoms at the time of clinic visits and during OLE when laboratory assessments are completed or an infusion is administered.

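### The only significance test under the primary safety hypothesis is a paired t-test of mean blood counts, which cannot support safety in 12 patients; the incidences that can inform it carry no interval

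*Combined protocol and SAP*

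**What the plan says.** Section 7.1 states that no power calculation was done, sets enrolment at 12, names the incidence of major infection and grade 3/4 cytopenias as the primary endpoint, and then says: "A paired t-test will be utilized to test the hypotheses described below".

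The first hypothesis that follows, in Section 7.2, is "Primary Hypothesis: Daratumumab is safe and well-tolerated in patients with PGNMID and C3GN associated with monoclonal gammopathy". Beneath it:

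- The incidence of major infection comes first and is to be reported.
- The cytopenias come next: "anemia, leukopenia, thrombocytopenia will be examined by evaluating changes in Hgb, WBC count and platelet count".
- Then comes the only significance test: "Statistical significance will be assessed using paired t-test comparing 6 months and 1 year value compared to baseline".
- Discontinuations for side effects are counted.

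The descriptive part of Section 7.2 says that "the number and proportion of patients with treatment-emergent major infections, grade 3 or 4 anemia, leukopenia or thrombocytopenia will be summarized". No interval is mentioned. The Study Summary repeats the pairing of incidence and test: "A paired t-test will be performed for changes in HgB, WBC count and platelet count from Baseline".

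Three other places matter:

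- The Primary Endpoints text at the end of Section 3.2 makes the blood count changes at 6 and 12 months part of the primary endpoint, so the t-test does have an endpoint to analyse.
- The section on subject populations defines one analysis set: "All-treated population: Any subject that received at least one dose of study drug".
- The Interim Analysis text and Section 8.4 stop the study if four patients have serious adverse events that lead to discontinuation of drug.

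No alpha, acceptable rate, safety margin or confidence interval is stated anywhere.

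**The concern.** The null hypothesis of the paired t-test is no mean change. Failing to reject it is absence of evidence, and with 12 patients that outcome is likely even when a real fall exists. The test also addresses the average patient, whereas the toxicity of interest is a severe event in a few patients. Large falls in a few patients move the mean a little and inflate the SD a lot.

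Timing adds to this. Section 8 schedules blood counts at eight post-baseline days, with cytopenias "evaluated initially by monthly CBC done on Day 21, 49, 77, 105, 133, 161" and then on Days 264 and 365. The test uses only the 6-month and 12-month values, and Day 365 is 365 − 162 = 203 days after the last scheduled infusion. Section 4.4.1 holds infusions for low counts until they improve. A transient severe cytopenia can therefore be absent from both tested values.

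The incidences do bear on safety, but they are to be shown as bare proportions. At stake is the basis of the primary conclusion: the only p-values attached to it cannot support it, and the results that could would not show how high a true rate 12 patients leave open.

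**Working it through.** There is no figure of the plan's own to reproduce, because 12 is given without alpha, power, effect size or SD.

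**Inputs.** From the plan: n = 12, one arm (Section 7.1); paired t-test at two times (Section 7.2); background rates of 11% for pneumonia, 18% for grade 3/4 thrombocytopenia and 19% for grade 3/4 anemia (Section 1.4). Assumed: two-sided 5%, because no alpha is stated; effects in units of the SD of change, because no SD is given; all 12 patients with both values.

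**1. Power of the paired t-test.** The critical value with 11 degrees of freedom is 2.201. The noncentrality for a mean fall of d SD is d × √12.

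- d = 0.5: noncentrality 0.5 × 3.464 = 1.732, power 0.353, so missed in 1 − 0.353 = 0.647 of trials.
- Power of 80% needs d = 0.889.
- The 95% interval for a mean change has half-width 2.201 / √12 = 0.635 SD.
- With 9 complete pairs, 80% power needs 1.07 SD and the half-width is 0.769 SD.

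**2. Large falls in a few patients.** Simulation, 400,000 trials per case: m patients change by N(−k, 1), the other 12 − m by N(0, 1). Here the SD is that of change in unaffected patients. Proportion of trials with a significant t-test:

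| Affected | k = 3 | k = 4 | k = 6 |
|---|---|---|---|
| 2 of 12 | 8.4% | 7.1% | 3.9% |
| 4 of 12 | 36% | 43% | 53% |

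The reason can be seen by hand. As k grows and dominates, the absolute t statistic tends to √(11m / (12 − m)). For m = 2 this is √(22/10) = 1.48, below 2.201, so ever larger falls in two patients do not produce significance. For m = 4 it is √(44/8) = 2.35, above 2.201, so detection rises. The decline with worsening falls belongs to the two-patient case and is not general.

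**3. What the incidences can show.** Exact (Clopper-Pearson) 95% intervals:

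- 0/12: 0 to 26.5% (upper limit 1 − 0.025^(1/12) = 0.265)
- 1/12: 0.2 to 38.5%
- 2/12: 2.1 to 48.4%

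The one-sided 95% upper bound for 0/12 is 1 − 0.05^(1/12) = 22.1%. By either bound, zero events would not exclude 11%, 18% or 19%. If those were the true rates, 0/12 would still occur with probability 0.89^12 = 24.7%, 0.82^12 = 9.2% and 0.81^12 = 8.0%.

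**4. The stopping rule beside the hypothesis.** Four of 12 is a 33% boundary. It counts serious adverse events that cause discontinuation. The primary endpoint counts major infections and grade 3/4 cytopenias, whether or not the drug is stopped. The documents do not link the two.

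**The case against.** The best defense is that the t-test is only one part of the safety assessment. Section 7.2 starts with infection incidence, adds the blood count changes, and ends with discontinuations. The changes are a listed primary endpoint, and a paired t-test is a standard analysis that can flag a mean fall. A grade 3/4 fall would be counted in the incidence, and counts below set limits are recorded as adverse events (Section 8.1). A proof-of-concept study needs no power calculation. Any reader can compute an exact interval from x/12. Finally, a mean change with a 95% interval is the same computation as the test: the interval excludes zero exactly when the two-sided 5% test rejects.

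Much of this stands. A reader might infer that the plan means to declare the drug safe if the t-tests are non-significant; the plan never says so. A reader might infer that the t-test is the whole safety analysis, or that there is no numeric safety rule at all; the incidence reporting and the four-patient stopping rule contradict both. The Section 1.4 rates are context only: that section does not name their population, the pneumonia figure is narrower than the major-infection endpoint, and this trial excludes myeloma and low baseline counts.

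What the defense does not answer is that Section 7.1 still names the t-test as the means of testing the hypotheses, no other criterion is linked to the safety hypothesis, and the informative results carry no statement of precision.

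**Conclusion.** The point holds and should be fixed. The only significance test under the primary hypothesis cannot support it: at 12 pairs a true mean fall of 0.5 SD is missed about 65% of the time, and two patients with falls of 3 to 6 SD would make it significant in only about 4 to 8% of trials. The incidences can inform safety, but even zero events leaves true rates up to 26.5% open, and the plan does not provide for saying so. The stopping rule limits harm during the trial without defining safe or using the primary events.

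The power figures rest on an assumed two-sided 5% and complete pairs. The two-patient falls are illustrative, since the documents give no SD. The exact intervals require only that all 12 patients are treated. The point does not call for a power calculation or more patients. Because the interval for mean change repeats the t-test's arithmetic, the real gain lies in the exact intervals on incidence and in no longer treating the t-test as the test of safety.

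**What to change.** In Section 7.1, Section 7.2 and the Study Summary:

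1. Remove the paired t-test as the test of the safety hypothesis. Report hemoglobin, white cell and platelet changes at 6 and 12 months descriptively, as mean change with 95% CI and number of pairs. State that a non-significant change is not evidence of safety.
2. Report each primary incidence in the all-treated population as x/n with an exact (Clopper-Pearson) 95% CI. Count grade 3/4 cytopenias from all scheduled blood counts, not only those at 6 and 12 months.
3. Word the primary objective as estimation of these incidences, and state in advance that 0/12 leaves true rates up to 26.5% not excluded.

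This changes wording and reporting only, with no new visits, samples or patients. The price is wide intervals (1/12 gives 0.2 to 38.5%), a less favorable safety statement, and no p-value for the primary hypothesis.

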1.2 Investigational Agent

Daratumumab is an IgG1-kappa human monoclonal antibody that binds to the CD38 transmembrane glycoprotein on the surface of tumor cells and induces apoptosis. This process is mediated through Fc mediated cross linking and immune-mediated cell lysis through complement dependent cytotoxicity, antibody dependent cell mediated cytotoxicity and antibody dependent cellular phagocytosis. It has an elimination half-time of 18 days and volume of distribution of 4.7L. Daratumumab is FDA approved for use in treatment of multiple myeloma, however is not approved for treatment of the condition under study, PGNMID and C3 GN associated with MG. The study was submitted by the Principal Investigator to the FDA for review and granted an IND Exemption.

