1.4 Dose Rationale and Risk/Benefits

The dose of daratumumab that has proven to be effective in patients with multiple myeloma is 16 mg/kg started once weekly for 8 weeks followed by every other week for 16 weeks, and then once every 4 weeks thereafter. We will be using similar dose (16 mg/kg) and similar dosing interval for a total of 16 doses over a 24 week period. The drug is only available to be administered intravenously and we aim to use the same route of administration.

Daratumumab overall is well-tolerated. The most common side-effect is infusion-related reaction (48%). We aim to use the same pre and post treatment regimen (including corticosteroid, diphenhydramine and acetaminophen) as has been done in the previous trials. Serious adverse effects include anemia, grade 3 or 4 (19%), lymphocytopenia grade 3 or 4 (40%), neutropenia, grade 3 or 4 (20%), thrombocytopenia, Grade 3 or 4 (18%), and increased risk of infection specifically pneumonia (11%). Common adverse effects include nausea (27%), anemia all grades (45%), lymphocytopenia all grades (72%), neutropenia all grades (60%), thrombocytopenia all grades (48%), backache (23%), cough (21%), upper respiratory infection (20%), fatigue (39%), fever (21%).

The treatment options for patients with PGNMID or C3GN associated with monoclonal gammopathy are limited with variable success. If untreated, majority of patients will progress to endstage renal disease. The current therapeutic options include rituximab vs. cyclophosphamide and prednisone with or without bortezomib. Daratumumab has a similar if not better side-effect profile to the above-mentioned treatment options and therefore we believe the risks associated with daratumumab are acceptable.

2 Study Objectives

Primary Objective

To assess the safety of daratumumab in patients with PGNMID or C3GN associated with monoclonal gammopathy.

Secondary Objective

To assess the efficacy of daratumumab in inducing complete or partial remission in patients with PGNMID or C3GN associated with monoclonal gammopathy as measured by change in proteinuria and serum creatinine.

3 Study Design

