3.1 General Design

This study is an open-label phase 2 trial of the safety and efficacy of daratumumab, in the treatment of PGNMID and C3GN associated with monoclonal gammopathy. Subjects will be screened at outpatient Nephrology Clinic visit appointments and interested qualified subjects will be consented and offered participation in this trial. Once consent has been obtained baseline values will be established and subjects will begin treatment and follow-up for the next 12 months. Daratumumab will be administered once weekly for 8 weeks and then once every 2 weeks for 8 additional doses. Patients will be followed for a total of 12 months (6 months after the last infusion). A final visit for evaluation and collection of lab samples will be conducted at the end of the study.

3.2 *The clinical course of the patients who have achieved complete or partial remission following daratumumab is unclear, therefore these patients who have consented to the OLE and achieved complete or partial remission, will be followed for 24 months following completion of the main trial. In the OLE, patients will be assessed every 3 to 6 months. Relapse is defined as a 30% increase in proteinuria from the lowest level the patient has achieved and will be documented with two 24 hour urine collections two weeks apart. If there is evidence of relapse, patients will receive 12 additional doses of daratumumab(16 mg/kg). The first 8 doses will be given weekly and the last 4 doses will be administered every other week. Primary Endpoints*

Incidence of major infection (defined as the development of pneumonia, severe urinary tract infection/pyelonephritis, sepsis, meningitis), grade 3 or 4 anemia, leukopenia or thrombocytopenia and changes in HgB, WBC count and platelet count from baseline to 6 month and 12 month timepoints.

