4.4 Early Withdrawal of Subjects

4.4.1 When and How to Withdraw Subjects

- Subjects decision to withdraw from the study (withdrawal of consent)
- Failure of subject to adhere to protocol requirements (missing more than two infusions within the first 8 weeks or more than three infusions in the following 4 months). If a patient experiences an adverse event and the PI determines the next dose must be delayed, the dose may be delayed for up to 4 weeks and continue on the protocol schedule without being withdrawn.
- Disease progression (> 50% increase in proteinuria and > 30% reduction in GFR as measured by creatinine clearance) at day 77 visit
- Severe infection (defined as the development of pneumonia, severe urinary tract infection/pyelonephritis, sepsis, meningitis)
- If Hgb < 8.0 g/dL or platelet < 50,000, or WBC < 3.0 or absolute neutrophil count (ANC) < 500, the infusion will be held and restarted once blood counts have improved.

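### The primary safety endpoint omits neutropenia and lymphocytopenia, and its paired tests do not show milder on-treatment falls in blood counts that recover before about Day 161

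*Combined protocol and SAP*

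**What the plan says.** The primary endpoint has two parts.

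- **Incidence.** Sections 3.2, 7.1 and 7.2 count major infections and grade 3/4 anemia, leukopenia and thrombocytopenia. Section 7.2 summarises them as treatment-emergent events, with no restriction to particular visits.
- **Change.** Section 3.2 lists "changes in HgB, WBC count and platelet count from baseline to 6 month and 12 month timepoints". Under the primary hypothesis, section 7.2 examines the cytopenias "by evaluating changes in Hgb, WBC count and platelet count, respectively", and adds "Statistical significance will be assessed using paired t-test comparing 6 months and 1 year value compared to baseline". Another sentence in 7.2 is looser: "Changes in Hgb, WBC count and platelet count from baseline (Day 0) will be analyzed through a paired t-test by comparing post-baseline to baseline values". It names no other time points, so 6 and 12 months are the only ones fixed.

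On what is expected, section 1.4 lists grade 3/4 lymphocytopenia at 40% and neutropenia at 20%. Section 8 opens with "The primary side effects associated with daratumumab include anemia, neutropenia and thrombocytopenia" and schedules blood counts on Days 21, 49, 77, 105, 133 and 161, then on Days 264 and 365. The section 6 schedule specifies a CBC with a five-part differential. An absolute neutrophil count (ANC) below 500 appears among the infusion-hold criteria (4.4.1) and the laboratory values to be documented as adverse events (8.1). Neither list has a lymphocyte threshold.

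**The concern.** White-cell toxicity enters the primary endpoint only as leukopenia and as change in total WBC. A total can stay up while one cell line falls. The protocol accepts this distinction, because 4.4.1 and 8.1 list ANC separately from WBC. A team following the plan exactly could report the primary safety result without stating how many patients had severe neutropenia or lymphocytopenia.

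The timing of the tests adds a second, smaller gap. They are the only formal analysis offered for the primary hypothesis, and they compare baseline with one late on-treatment value and one value long after treatment. A non-significant result could be read as no effect on blood counts when a moderate fall had occurred earlier and resolved.

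**Working it through.** The plan has no power, alpha, standard deviation or effect size to reproduce; section 7.1 states that no power calculation was done. The check therefore covers coverage, expected counts and timing.

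**1. Coverage by cell line**

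| Count | Grade 3/4 rate in 1.4 | Primary incidence | Paired test | AE threshold in 8.1 |
|---|---|---|---|---|
| Hemoglobin | 19% | yes | yes | < 8.0 g/dL |
| Platelets | 18% | yes | yes | < 50,000 |
| Total WBC | none given | yes (leukopenia) | yes | < 3.0 |
| Neutrophils | 20% | no | no | ANC < 500 |
| Lymphocytes | 40% | no | no | none |

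The cytopenia with the highest quoted grade 3/4 rate has the least coverage.

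**2. Expected cases at n = 12** (section 7.1), using the 1.4 rates. Expected number = n × p; chance of at least one = 1 − (1 − p)^n.

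- Neutropenia: 12 × 0.20 = 2.4; 1 − 0.8^12 = 93.1%.
- Lymphocytopenia: 12 × 0.40 = 4.8; 1 − 0.6^12 = 99.8%.

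**3. Timing.** The nearest scheduled count to 6 months is Day 161, and 12 months is Day 365. The tests thus use 2 of 8 post-baseline counts and 1 of 6 on-treatment counts. Days 21 to 133 are unused.

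- Day 161 is the day before infusion 16 (Day 162; sections 4.3 and 6), so it is an on-treatment value.
- Day 365 is 365 − 162 = 203 days after the last dose. Section 1.2 says of the drug: "It has an elimination half-time of 18 days". So 203 / 18 = 11.3 half-lives, and 0.5^11.28 = 0.0004, or about 0.04% of the last dose.

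**4. What a test at Day 161 can see.** Assume an on-treatment fall of 1.5 within-patient SD, two-sided alpha 0.05 and 12 complete pairs. If a fraction f of the fall remains at Day 161, the standardised change is 1.5f/√2. Noncentral-t power (11 df, noncentrality = standardised change × √12) is 92% for f = 1, 39% for f = 0.5 and 5% for f = 0. A fully recovered fall gives no signal beyond the false-positive rate.

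**5. Why the added data should not be tested.** The plan now has 3 counts × 2 times = 6 tests. At 0.05 each, if independent, the chance of any false positive is 1 − 0.95^6 = 26%. Five counts at six on-treatment visits would be 30 tests, and 1 − 0.95^30 = 79%. Testing each patient's lowest value is worse. In simulation with no true change and independent normal within-patient error, the lowest of six values lies on average 1.27 within-patient SD below a single baseline, and a paired t-test at n = 12 rejects in about 92% of trials.

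**The case against.** Much can be said for the plan as written.

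- **The primary endpoint does not miss the on-treatment low point altogether.** A reader might infer that it does. The incidence part is not tied to 6 or 12 months, and monthly counts can detect grade 3/4 anemia, leukopenia and thrombocytopenia during treatment. Section 7.2 also reports discontinuations for falling counts. This stands; only the size of lesser falls is lost.
- **The 6-month value is not a recovery reading.** It follows 15 infusions. Summing 0.5^((t − dose day)/18) over the section 6 infusion days, in units of one dose, gives 1.62 at Day 105, 1.51 at Day 133 and 1.47 at Day 161, so Day 161 resembles the two visits before it. Weekly dosing ends on Day 50, so only Days 21 and 49 fall in the weekly phase. This also stands.
- **The hold rule does not make Day 161 a set of recovered patients.** Section 4.4.1 says "the infusion will be held and restarted once blood counts have improved", so some early low counts may have resolved by then. But the rule touches only patients below its limits, and a low count can first appear at Day 161.
- **Neutrophils are not ignored.** Section 8 commits to evaluating neutropenia at the monthly counts, ANC < 500 is documented as an adverse event, and section 7.2 promises descriptive statistics for all variables as appropriate. This is true, but none of it places neutropenia in the primary endpoint, and lymphocytes have no threshold at all.
- **The rates may not transfer.** The trials described in section 1.3 were in refractory myeloma, whereas section 4.2 excludes myeloma, WBC < 3.5 and platelets < 100,000. The expected counts are therefore only illustrative.
- **Low drug level does not prove that counts have recovered.** The documents do not say that counts track drug level, and persistent cytopenia at 12 months is a fair safety question. Day 365 should be kept and labelled for what it is.

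**Conclusion.** The point holds in two parts of unequal weight.

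The firmer part is the omission. Neutropenia and lymphocytopenia, which the protocol itself expects, are in neither the incidence list nor the change tests of the primary endpoint, although the data will be collected. If the section 1.4 rates applied, about 2.4 and 4.8 of 12 patients would have grade 3/4 events with no named place in the primary result. That rests on background rates carried over to a different population.

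The lesser part is timing. The paired tests cannot show the size of milder falls that recover before about Day 161. This rests on reading 6 months as Day 161, and the power figures rest on an assumed fall and an assumed alpha.

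Two stronger readings are not supported. The plan does not look only at times when a drug effect would be hard to see: that may fit Day 365 but not Day 161. Nor can a case such as ANC 400 with WBC 3.2 be used to show that the endpoint fails. The WBC limit of 3.0 is the hold and adverse-event threshold, not the grade 3/4 definition in the endpoint, and such a patient is documented as an adverse event.

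The weight is moderate: this is an unpowered proof-of-concept study, but safety is its primary objective and the remedy is cheap.

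**What to change.** In sections 3.2 and 7.2:

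1. Add grade 3 or 4 neutropenia and lymphocytopenia to the primary incidence table, each with an exact confidence interval, and name the grading scale; none is named now. With 12 patients the intervals will be wide. For example, 2 of 12 gives 2.1% to 48.4% (Clopper–Pearson 95%: the 0.025 quantile of Beta(2, 11) and the 0.975 quantile of Beta(3, 10)).
2. Summarise hemoglobin, platelets, total WBC, ANC and absolute lymphocyte count at each scheduled visit from Day 21 to Day 161 as mean change from baseline with a confidence interval. Add no t-tests.
3. List each patient's lowest Day 21 to 161 value for each count, descriptively, with no test on it.
4. Label Days 264 and 365 as post-treatment or recovery readings.

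The cost is protocol wording and a few more table rows; the differential is already scheduled, so no blood draw is added. The safety profile may look less favourable because more cytopenias will be shown. No change to the hold or withdrawal rules is proposed.
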